## LIST OF ABBREVIATIONS

AE	Adverse Event/Adverse Experience
BPG	Benzathine Penicillin G
CFR	Code of Federal Regulations
CMS	Clinical Material Services
CoC	Certificate of Confidentiality
CROMS	Clinical Research Operations and Management Support
CSR	Clinical Study Report
DFA-TP	Direct Fluorescence Antibody- Treponema pallidum
DHHS	Department of Health and Human Services
DMID	Division of Microbiology and Infectious Diseases
DSMB	Data and Safety Monitoring Board
eCRF	Electronic Case Report Form
EMR	Electronic Medical Record
FDA	Food and Drug Administration
FWA	Federal Wide Assurance
GCP	Good Clinical Practice
HIV	Human Immunodeficiency Virus
IATA	International Air Transport Association
ICF	Informed Consent Form
ICH	International Conference on Harmonisation
ICON	ICON Clinical Research, Inc.
IDES	Internet Data Entry System
IM	Intramuscular
IND	Investigational New Drug Application
IRB	Institutional Review Board
ISM	Independent Safety Monitor
ITT	Intent-to-Treat
IV	Intravenous
MedDRA®	Medical Dictionary for Regulatory Activities
MOP	Manual of Procedures
MSM	Men who have Sex with Men
MU	Million Units
N	Number (typically refers to subjects)
NAT	Nucleic Acid Test
NIAID	National Institute of Allergy and Infectious Diseases
NIH	National Institutes of Health
OER	Office of Extramural Research, NIH, DHHS
OHRP	Office for Human Research Protections
P&S	Primary and Secondary
PASS	Power Analysis and Sample Size Software
PCR	Polymerase Chain Reaction

PI	Principal Investigator
RCT	Randomized Controlled Trial
RPR	Rapid Plasma Reagin
QA	Quality Assurance
QC	Quality Control
SAE	Serious Adverse Event/Serious Adverse Experience
SAS	Statistical Analysis System
SDCC	Statistical and Data Coordinating Center
SOP	Standard Operating Procedure
STI	Sexually Transmitted Infection
STI CTG	Sexually Transmitted Infections Clinical Trials Group
STS	Serological Test for Syphilis
TRI	Technical Resources International, Inc.
US	United States

---

## PROTOCOL SUMMARY

Title:	A Phase 4 Comparative Trial of Benzathine Penicillin G 2.4 Million Units Administered as a Single Dose versus Three Successive Weekly Doses for Treatment of Early Syphilis in Subjects with or without HIV Infection
Phase:	4
Population:	Approximately 560 adults aged 18 years or older with untreated early (primary, secondary, or early latent) syphilis (to achieve 420 evaluable subjects)
Number of Sites:	Ten
Study Duration:	48 months
Subject Participation Duration:	12 months
Description of Agent or Intervention:	Benzathine penicillin G (BPG) 2.4 million units (MU) injected once (Arm 1) or weekly for three successive weeks (Arm 2)
Objectives:	
Primary:
 

• To compare the serological response to therapy in subjects with early (primary, secondary, or early latent) syphilis treated with BPG 2.4 MU once or weekly for three successive weeks

 
Secondary:
 

• To determine if the difference in response to therapy between treatment arms by Month 6 differs among subjects with or without HIV infection

• To determine the impact of multiple BPG injected doses on subject compliance with study product and adherence to the corresponding scheduled visits

• To determine the incidence and manifestations of the Jarisch-Herxheimer reaction among subjects treated for early syphilis with BPG

• To collect prospective data up to Month 12 on the serological response to therapy in subjects treated for early syphilis with either BPG regimen

• To compare epidemiological characteristics of early syphilis among subjects with or without HIV infection

[figure not shown]
**Description of Study Design:**

BPG 2.4 MU injected either once (Arm 1) or weekly for three successive weeks (Arm 2) as determined by randomization, with follow-up visits at Months 1, 3, 6, 9, and 12 for safety, clinical, and laboratory assessments

**Estimated Time to Complete Enrollment:**

36 months

## 2 BACKGROUND INFORMATION AND SCIENTIFIC RATIONALE

### 2.1 Background Information

Despite syphilis being a major public health problem for well over a century, and its treatment recommendations being unchanged for nearly 50 years, questions about syphilis and its management are amongst the most common questions to arise regarding sexually transmitted infections (STIs). The human immunodeficiency virus (HIV) epidemic has compounded these problems, as syphilis is now appreciated as both a risk marker and risk factor for HIV acquisition, and case reports and uncontrolled case series have led to recurring, unresolved questions regarding the optimal management of syphilis with respect to treatment regimens, serological follow-up, and risks for treatment failure [1]. Syphilis in the US is resurging, with rates of primary and secondary (P&S) syphilis increasing by 74% from 2012 to 2016 and disproportionately among HIV-infected persons [2]. Further rising P&S rates in women led to a 28% increase in congenital syphilis cases in the US between 2015 and 2016 [3]. No large prospective studies in the US have provided data on outcomes of recommended single-dose penicillin therapy versus widely-used but unstudied multiple-dose therapy for persons with early syphilis and HIV co-infection for over 30 years. In addition, there are no contemporary data describing serological responses to syphilis therapy at >6 months following therapy, raising questions as to how to best follow the ~20% of “serofast” patients who fail to serologically respond at >6 months following therapy. These questions represent a pressing public health need that is best addressed through a multicenter, randomized clinical trial (RCT).

Infections due to *Treponema pallidum* are the third most commonly reported infection in the US and are a global public health priority. Currently, P&S syphilis rates in the US are increasing faster than for any other reportable STI, and over half of P&S syphilis cases in men who have sex with men (MSM), the group that accounts for most new cases, are occurring among persons with HIV co-infection [3]. Untreated syphilis is a significant cause of morbidity in children born to mothers with untreated infection, may cause serious neurological or cardiovascular disease, and is both a proven risk factor and risk marker for HIV acquisition. Syphilis also remains a glaring example of STI health disparities, with P&S syphilis rates among African Americans in the US being more than six times those of non-Hispanic whites [4].

Penicillin is currently the only recommended treatment for syphilis (alternative therapies may be used in persons with penicillin allergy [5]). However, recent studies have shown that ~20% of persons treated for early syphilis with recommended, single-dose BPG 2.4 MU are “serofast” (do not show the desired 4-fold decline in serological test for syphilis titers 6 months following therapy) [5, 6], and concerns have been raised as to whether this regimen adequately treats early syphilis in HIV-infected persons. A well-conducted, multicenter RCT in the 1990s showed that higher doses of penicillin given in combination with the recommended BPG regimen did not

---

significantly change the serological response to therapy at 3, 6, or 12 months [7], but there are no RCTs evaluating whether a longer duration of BPG therapy improves the serological response to therapy among persons with or without HIV infection. While this earlier study addressed questions regarding daily penicillin doses for early syphilis treatment, the question of duration remains unresolved. As a result, there is substantial variation in the treatment of early syphilis, with many providers using multiple injected doses of BPG or treating serofast persons who have no evidence of active infection.

## **2.2 Rationale**

Epidemiologically, syphilis infections tend to shift from one risk group to another. Past syphilis epidemics in the US have occurred in heterosexual men and women, or MSM. More recently, syphilis rates in the US have more than doubled over the past decade and now occur disproportionately among HIV-infected persons [4].

While penicillin is generally regarded as highly effective for syphilis treatment, whether or not currently recommended therapy is equally effective for persons with or without HIV infection remains unclear. In addition, recent appreciation of the fact that ~20% of persons treated for early syphilis are serofast has raised concerns regarding the significance of this observation [6]. Some clinicians believe that the serofast state signifies treatment failure, while others believe it represents failure to serologically respond to therapy in successfully treated patients. Each of these concerns may lead to inadequate therapy or over treatment in persons with early syphilis, as well as much confusion among clinicians about appropriate therapy.

The primary aims of this study are to determine whether subjects with or without HIV infection benefit from a longer duration of therapy (BPG 2.4 MU weekly for three successive weeks instead of as a single dose), and whether subjects with or without HIV infection differ in their response to BPG therapy for early syphilis.

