## 3 OBJECTIVES

### 3.1 Study Objectives

#### 3.1.1 Primary Objective

- To compare the serological response to therapy in subjects with early (primary, secondary, or early latent) syphilis treated with BPG 2.4 MU once or weekly for three successive weeks

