## 11 STATISTICAL CONSIDERATIONS

### 11.1 Study Hypotheses

The primary objective of the study is to compare the serological response to therapy in subjects with early (primary, secondary, or early latent) syphilis treated with BPG 2.4 MU once or weekly for three successive weeks. In particular, the objective is to demonstrate noninferiority of the one-dose regimen compared to the three-dose regimen and to also assess noninferiority within the HIV status subgroups (HIV-infected and HIV-uninfected subjects). See Section 11.4.4 for the definition of serological response.

The null hypothesis for the primary objective is that the difference in serological response rate between the three-dose and one-dose groups is at least 10%, and the alternative hypothesis is that the difference in response rates is less than 10%. The null and alternative hypotheses for the secondary HIV status subgroup objective are defined similarly.

Note that tests will be performed and p-values will be reported for secondary analyses for informational purposes and not to make definitive claims. The study is intended and designed to formally test the primary hypothesis only, and so no corrections for multiplicity are planned.

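### Section 2.2 asks whether subjects benefit from three doses, but the protocol prespecifies no confirmatory conclusion for an observed advantage of three doses

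*Protocol*

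**What the plan says.** The background and rationale pose a question about benefit. Section 2.1 says that "there are no RCTs evaluating whether a longer duration of BPG therapy improves the serological response to therapy" among persons with or without HIV infection. Section 2.2 follows with a primary aim, to find out whether subjects "benefit from a longer duration of therapy (BPG 2.4 MU weekly for three successive weeks instead of as a single dose").

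The listed primary objective in Section 3.1.1 is neutral: "To compare the serological response to therapy in subjects with early (primary, secondary, or early latent) syphilis treated with BPG 2.4 MU once or weekly".

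Section 11.1 then narrows it: "the objective is to demonstrate noninferiority of the one-dose regimen compared to the three-dose regimen". The null is that "the difference in serological response rate between the three-dose and one-dose groups is at least 10" percent, and "the alternative hypothesis is that the difference in response rates is less than 10" percent. The same section says that p-values from secondary analyses are informational and not a basis for definitive claims, and that "The study is intended and designed to formally test the primary hypothesis only".

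Section 11.4.4.1 places in the primary analysis, in the ITT population, a Farrington-Manning test at one-sided 5%, together with the difference in proportions and its 95% confidence interval. It also plans a Cochran-Mantel-Haenszel comparison of the arms and labels it secondary and corroborative.

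**The concern.** Whether subjects benefit from the longer course is a question about superiority of three doses. The single formal test looks the other way. Rejecting its null shows that any benefit is below 10 points. Failing to reject it establishes nothing, and in particular does not establish benefit. The one planned test of any difference between the arms, the Cochran-Mantel-Haenszel test, is a secondary analysis and so falls under the restriction in Section 11.1.

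The declared aim can therefore be answered formally in one direction only. If three doses do raise the response rate, the trial has an estimate and an interval but no rule, fixed in advance, that lets it conclude so. A superiority statement made after the data are known would be open to the charge of being post hoc, although the same data could have supported a prespecified one at no cost.

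**Working it through.** **Inputs.** From Sections 11.1, 11.2 and 11.4.4.1: margin 0.10; one-sided alpha 0.05; response 0.788 in both arms under the alternative; 1:1 allocation; 210 evaluable per arm; 560 enrolled, that is 280 per arm if all enter the ITT analysis. Assumed here: true three-minus-one differences of 0, 5, 10 and 15 points with the three-dose rate held at 0.788, and ITT response rates not altered by imputation.

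**The plan's own figure.** The Farrington-Manning restricted estimates at the margin are 0.7297 and 0.8297.
- Null SE = √[(0.7297×0.2703 + 0.8297×0.1703)/210] = 0.04015.
- SE under the alternative = √(2×0.788×0.212/210) = 0.03989.
- Power = Φ[(0.10 − 1.645×0.04015)/0.03989] = Φ(0.851) = 80.3%. Exact binomial enumeration gives 80.4%.
- 420/(1 − 0.25) = 560.

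The stated sample size reproduces.

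**What an observed difference would lead to** (approximate, rates near 0.788).
- 210 per arm: noninferiority is met below 0.10 − 1.645×0.03989 = 3.4 points. The 95% interval lies above zero beyond 1.96×0.03989 = 7.8 points.
- 280 per arm: SE = √(2×0.788×0.212/280) = 0.03454, giving 4.3 and 6.8 points.

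The two regions do not overlap at either size. Example: 78.8% against 63.8% observed with 210 per arm gives SE = √[(0.788×0.212 + 0.638×0.362)/210] = 0.0435 and an interval of 15 ± 8.5, or 6.5 to 23.5 points. Noninferiority fails and the advantage is plain, yet the protocol draws no conclusion from it.

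**Chance of a superiority conclusion at one-sided 2.5%, true rates 0.688 and 0.788, 210 per arm.**
- Pooled null SE = √(2×0.738×0.262/210) = 0.04291.
- SE under the alternative = √[(0.688×0.312 + 0.788×0.212)/210] = 0.04263.
- Power = Φ[(0.10 − 1.96×0.04291)/0.04263] = Φ(0.373) = 64.5%.

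Exact enumeration gives 64.8% with the pooled z test and 65.2% with a simple unpooled interval, so the choice of interval hardly matters. Exact results for the three practical conclusions:

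| Per arm | True difference | One dose noninferior | Three doses superior | Neither |
|---|---|---|---|---|
| 210 | 0 | 80.4% | 2.5% | 17.1% |
| 210 | 5 points | 33.0% | 22.5% | 44.5% |
| 210 | 10 points | 5.1% | 64.8% | 30.1% |
| 210 | 15 points | 0.3% | 92.9% | 6.9% |
| 280 | 0 | 89.4% | 2.5% | 8.0% |
| 280 | 5 points | 40.2% | 28.6% | 31.2% |
| 280 | 10 points | 5.0% | 77.2% | 17.8% |
| 280 | 15 points | 0.2% | 97.7% | 2.1% |

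Both conclusions together have probability below 10⁻¹⁰ in every row.

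**Multiplicity.** The nulls are a difference of at least 10 points and a difference of at most 0. They are disjoint, so at most one can be true and at most one false rejection is possible. The familywise error is that of whichever null holds: 5.0% to 5.1% at a 10-point difference and 2.5% at zero. Strictly between 0 and 10 points neither null is true.

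**The case against.** The other side has five arguments, and much of them stands.

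- *The advantage would be reported.* A reader might infer that even a clear benefit of three doses could not be claimed at all, or would appear only as a failure to show noninferiority. The protocol does not support that. The 95% interval belongs to the primary analysis, and the informational-only sentence is about secondary analyses. Only the confirmatory status is missing.
- *The aim sits in background prose.* Section 2.2 is rationale. Section 3.1.1 is neutral and Section 11.1 specifies it, so the controlling sections agree with each other. This lowers the weight of the point but does not remove it, because Section 2.2 calls the benefit question a primary aim of the study.
- *Noninferiority is a fair approach.* Section 2.3.1 describes the single dose as the currently recommended therapy, and Section 2.2 worries about both under- and over-treatment. Excluding a benefit of 10 points or more answers part of the question. It cannot answer it in the affirmative.
- *Interpretation rules often sit in the SAP.* True, and the SAP has not been seen. But Section 11.1 itself limits the formal hypotheses to one, so an SAP rule granting a superiority claim would conflict with it.
- *The failure rate is not a flaw.* One might be tempted to count it against the design that noninferiority is missed about 95% of the time at a true 10-point benefit. That is simply the 5% type I error at the edge of the null, as intended.

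**Conclusion.** The point holds as a gap between the stated aim and the formal inference. It is not an error in the test, the margin, the alpha level or the sample size. The protocol would show a three-dose advantage but has no prespecified confirmatory conclusion for it.

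With a three-dose rate of 0.788, adding the superiority reading yields that conclusion in about 65% to 77% of trials for a true 10-point benefit and 93% to 98% for 15 points (210 to 280 per arm). The gain is in inferential status: these are essentially the trials in which the planned interval would exclude zero anyway.

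The figures depend on the assumed rates. For 88.8% against 78.8% the normal approximation gives 79.6% at 210 per arm and 89.7% at 280. The 280-per-arm figures also require all 560 subjects in the ITT analysis, with response rates unaffected by imputation. None of this bears on which regimen is preferable.

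**What to change.** In Sections 11.1 and 11.4.4.1, and correspondingly in the SAP:

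1. State that, on the same ITT comparison, three doses will be concluded superior if the planned two-sided 95% interval for the three-dose minus one-dose difference lies wholly above zero (one-sided 2.5%). Noninferiority remains judged by the Farrington-Manning test at one-sided 5%.
2. State that no multiplicity adjustment is needed because the two nulls are disjoint.
3. Exempt this reading from the sentence that makes secondary p-values informational, and amend the statement that only one hypothesis is formally tested.
4. List the practical conclusions: one dose noninferior, three doses superior, or inconclusive. Both together is logically possible but has essentially zero probability at 210 to 280 per arm with a three-dose rate of 0.788.

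At minimum, if the sponsor wants a single formal hypothesis, reword the aim in Section 2.2 to match the noninferiority objective in Section 11.1.

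The cost is wording. Either route needs no more subjects and leaves noninferiority power unchanged; the first uses an interval already planned. The superiority rule should be in place before outcome data are seen by arm.

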## **2.3 Potential Risks and Benefits**

### **2.3.1 Potential Risks**

The risks associated with participation in the study are small. Penicillin is widely used to treat syphilis and other infections and is relatively well tolerated. All subjects in the trial will receive at least the currently recommended therapy. The most common adverse events (AEs) caused by penicillin include rash and hypersensitivity reactions. Therapeutic outcome is not a major concern, as all subjects will receive at least the Centers for Disease Control and Prevention-recommended dose of BPG for early syphilis. Subjects randomized to receive two additional injected doses of BPG will be at risk for additional discomfort and bruising at injection sites. Subjects may feel temporary pain or discomfort during blood draws, and there is a small risk of

infection at the site of the blood draw.

Information concerning subjects' sexual history is necessarily detailed given the study's objectives and may provoke some minor psychological or emotional stress when requested; subjects who receive a new diagnosis of an STI during the study may also experience minor psychological or emotional stress. Female subjects will be cautioned about the potential hazard of becoming pregnant and advised to use adequate birth control methods for the entire duration of their participation in the trial.

### **2.3.2 Known Potential Benefits**

Subjects may benefit from this study by finding out more about the specific cause of symptoms they may be experiencing. Subjects may benefit from pre- and post-test counseling, treatment, and referrals, as necessary. It has previously been observed that subjects are empowered by knowing, for example, more about what syphilis is and how it can be prevented.

---

## 3 OBJECTIVES

### 3.1 Study Objectives

#### 3.1.1 Primary Objective

- To compare the serological response to therapy in subjects with early (primary, secondary, or early latent) syphilis treated with BPG 2.4 MU once or weekly for three successive weeks

#### 3.1.2 Secondary Objectives

- To determine if the difference in response to therapy between treatment arms by Month 6 differs among subjects with or without HIV infection
- To determine the impact of multiple BPG injected doses on subject compliance with study product and adherence to the corresponding scheduled visits
- To determine the incidence and manifestations of the Jarisch-Herxheimer reaction among subjects treated for early syphilis with BPG
- To collect prospective data up to Month 12 on the serological response to therapy in subjects treated for early syphilis with either BPG regimen
- To compare epidemiological characteristics of early syphilis among subjects with or without HIV infection

### 3.2 Study Outcome Measures

#### 3.2.1 Primary Outcome Measure

- The proportion of subjects in each treatment group with a 4-fold decline in rapid plasma reagin (RPR) titers or seroreversion, simultaneously measured in sera collected throughout study participation at a single reference laboratory, by Month 6

#### 3.2.2 Secondary Outcome Measures

- The proportion of subjects in each treatment group with a 4-fold decline in RPR titers or seroreversion by Month 6 among subjects with or without HIV infection
- The proportion of subjects in each treatment group with a 4-fold decline in RPR titers or seroreversion by Month 12
- The proportion of subjects in each treatment group with a 4-fold decline in RPR titers or seroreversion by Month 12 among subjects with or without HIV infection
- The proportion of subjects (overall and in each treatment group) who receive all assigned doses within the assigned visit windows
- The proportion of subjects in each treatment group who report Jarisch-Herxheimer reaction manifestations (fever, intensification of rash, myalgia, and other systemic symptoms) occurring within approximately 24 hours of initial BPG administration
- Demographics, sexual history, and socio-epidemiologic characteristics at baseline and sexual history through Months 6 and 12 among subjects with or without HIV infection and overall

## 4 STUDY DESIGN

This is a Phase 4, open-label, multicenter trial to evaluate the efficacy of a single injected dose of BPG 2.4 MU (Arm 1) compared to three successive weekly injected doses of BPG 2.4 MU (Arm 2) for treatment of early syphilis in HIV-infected and HIV-uninfected subjects. Subjects will be aged 18 years or older with untreated early syphilis (primary, secondary, or early latent as defined in prior syphilis treatment trials of the Sexually Transmitted Infections Clinical Trials Group (STI CTG)). The study will be conducted at 10 sites in the US and will enroll approximately 560 subjects to achieve 420 evaluable.

The study will involve a screening/enrollment visit and seven scheduled follow-up visits (Weeks 1 and 2, and Months 1, 3, 6, 9, and 12) over a 12-month period. At the enrollment visit, after providing informed consent, all subjects will undergo a brief sexual and medical history and a directed physical examination; all women of childbearing potential will have a urine or serum pregnancy test performed as part of qualification for study participation; all subjects will undergo phlebotomy for serological testing for syphilis and HIV according to the study and clinic protocols. All subjects who have not been tested for chlamydia and gonorrhea since last sexual activity and all subjects who have been sexually active in the past 14 days will have specimens collected for chlamydia and gonorrhea testing. Subjects will have specimens collected for other STI testing as indicated by local standard of care and subject history. All eligible subjects will be randomized to Arm 1 or Arm 2 and will receive an injected dose of BPG 2.4 MU.

Study personnel will attempt to contact subjects approximately 24 hours after Visit 1 to assess for symptoms of a Jarisch-Herxheimer reaction as described in Section 8.1. At the second and third visits (Weeks 1 and 2 of follow-up), subjects randomized to Arm 2 will receive injected doses of BPG 2.4 MU.

At all follow-up visits, subjects will have an interval history obtained, undergo a directed physical examination, and have repeat specimens collected for STI testing (based on the subject history and clinic protocols). At all follow-up visits, subjects will undergo phlebotomy for serological testing for syphilis and serum storage. At the Month 3, Month 6, Month 9, and Month 12 follow-up visits, consenting HIV-uninfected subjects will be tested for HIV infection using a 4th generation serological test for HIV. At Visit 1, study staff will swab consenting subjects' oral cavities and primary or secondary lesions (if lesions are present per Section 5.1); see Section 8.2.2.

Safety will be measured by subject report and physical examination (including vital signs: temperature, heart rate, respiration rate, and blood pressure; and genital, rectal, oral, skin, and lymph node examinations). All AEs (including solicited reactogenicity AEs and other unsolicited AEs) will be recorded through Month 1. Safety oversight will be provided by a

Data and Safety Monitoring Board (DSMB) and site Independent Safety Monitors (ISMs) as described in Section 9.6.

While sites will perform their own serological testing as needed for subject management, serological testing to determine study outcomes and serum banking will be performed at the Central Laboratory (University of Alabama at Birmingham).

The duration of the study for each subject will be 12 months. Enrollment is expected to be completed in 36 months. For additional details on study procedures/evaluations and study schedule by study visits, see Sections 7 and 8 and Appendix A.

